b. Baseline Screening and Enrollment. As with our previous work, the baseline screening will occur within a week to reduce the potential for change in depression over time. Subjects will be able to come to the Loyola School of Nursing (SON) Research Room in Maywood, IL on weekday or Saturdays. Women will fast for 10 hours prior to their appointment (they will be allowed to drink water) and to bring their supplements with them. They will be informed that first baseline testing will last between 2 and 3 hours and subsequent visits will last between 1 to 2 hours. Upon arrival at the site, informed consent will be obtained and their blood will be drawn by a study nurse. The physical measures (i.e. weight and height) will then be done. Study subjects will then be provided breakfast, reminded to take their prescribed supplements, and instructed to complete the questionnaires. The researcher will review the questionnaires for missing data and assess if the items were skipped or not answered due to personal choice.

The diagnostic interview schedule (based on the DSM-IV) to assess current and past mental health will be administered by a trained study nurse (25 to 30 minutes). Exclusionary criteria such as bipolar and psychotic disorders and alcohol/substance abuse will be verified. Active suicidal ideation will also be assessed using a form developed by [name] (attached). If a participant has active suicidal ideation, [name], psychiatrist and co-investigator and/or [name], psychologist and co-investigator, will be contacted and the safety protocol followed (See Human Subjects). These subjects will not be enrolled. The same procedures will be implemented at all follow-up visits. In addition, if the patient answers question #9 on the PhQ-9 depression tool with a response other than "Not at all", the suicide assessment form will also be completed on these patients as well and similar procedures followed if active suicidal ideation.

At the baseline visit, both groups will receive a list of resources for mental health services developed by the psychiatrist (as with our previous study) as they will not be prevented from getting help if needed as a safety measure. In our previous depression study, this occurred infrequently (<3%), as 1 woman started an antidepressant and 1 woman restarted therapy.

Prior to leaving the data collection site, the participants will be asked to partake in a brief history and physical that will be conducted by a trained health care professional. This assessment will take 20 minutes.

c. Study Visits. Following the first visit, the lab tests (vitamin D, calcium, PTH, Cardiometabolic profile as recommended by the FDA) will be reviewed by [name], endocrinologist and co-investigator to ensure that blood enrollment criteria are met. If so, the patient will be scheduled for a second visit within 10 days of their initial visit. At that visit, the patient will have a body composition scan to assess for body composition (which includes bone, lean and fat mass) which should take 30 minutes. Prior to the scan, a pregnancy test will be administered to ensure the subject is not pregnant (see human subjects). Upon completion, a small conference room at that site will be used for the research nurse to provide the study supplement, review the weekly schedule, and discuss all subsequent contacts (phone and scheduled visits). The study nurse will also review potential side effects and reiterate the reproductive risks associated with the treatment at baseline visit 2 and 3 month visit when the supplement is provided. The patient will be told that an automated message (preferred as phone, e-mail or text) will remind them to take their weekly supplement. They will be informed that at three and six months, they will return for data collection of physical measurements and questionnaires. They will be told that in the months (2, 4,) when they don't have a scheduled visit, the study nurse will conduct a formal phone call follow-up where they will be asked about their compliance, side effects, and be screened for their depressive symptoms (CES-D). These procedures will be followed for all phone call visits (Appendix).

Upon completion of these verbal and written instructions, the supplement will be dispensed. There will be a total of 12 pills for the period of 12 weeks. Following the dispensing directions, the nurse will ask the subject if they have any questions to ensure there is an understanding and to call the study nurse if questions arise.

The third visit (three months following initiation of treatment) will occur at the SON. The protocol established at baseline will be followed by the nurse (blood will be drawn, physical measures, questionnaires, and interview). Questionnaires that do not address mental health will be sent to participants prior to their visit with a reminder appointment letter. This is to limit the time spent onsite for data collection. It will not be mandatory that they bring them completed as they can complete them onsite if they so choose. The nurse will also request the study bottle and count the remaining pills (if any). If supplement is remaining, the nurse will record the reasons and the bottle will not be returned to the patient. All study questionnaires will be reviewed. Upon completion of these procedures, study supplement will be dispensed and the protocol for taking the supplement will be reviewed. To protect subjects, their depression level will be assessed and safety protocol implemented (if needed) using the same procedures described at baseline. The labs drawn at this time will be reviewed by the endocrinologist to inform the PI if patients need to stop their prescribed therapy (Study Design: Safety-1e). The fourth and final visit (six months following initiation of treatment) will occur at the SON. The patient will have the following assessed at end of study: vital signs, weight, walk test, neurosensory exam of feet, and assessment for any complaints. Questionnaires will be administered and reviewed as delineated in the protocol as well. The participant will be informed of optional interview at the six month visit. An optional informed consent will be signed at the time of the interview and participants will also complete the family questionnaires. The procedures previously described will be followed, although no supplement will be dispensed and patients will be informed to follow-up with the primary care provider regarding future supplementation. The patient will be sent their study lab tests (performed by Quest) and DEXA scan in the mail, informed that the dose of the medication will not be known until the end of the study, thus following up with their healthcare provider for future dosing of vitamin D is recommended. Letter to study participant is attached.

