Hypothesis 1a: Depressive symptoms will be associated with poor family functioning.

Hypothesis 1b: Higher depressive symptoms will be associated with poor FQOL.

Hypothesis 3c: Depressive symptoms mediate the relationship of family functioning and FQOL.

Aim 3: Determine the relationship of family functioning, self-management and FQOL.

Hypothesis 2a: Better family functioning will be associated with more self-management behaviors.

Hypothesis 2b: Better family functioning will be associated with better FQOL.

A sub-study was added to investigate the urinary microbiome and lower urinary tract symptoms in women with type 2 diabetes titled “The Urinary Microbiome and Vitamin D in Women with Type 2 Diabetes” study has recently been submitted for review for potential funding to Novo Nordisk under LU# 208880.

This sub-study of the Sunshine 2 Study has the following specific aims:

Primary Objectives: (1) To determine the FUM composition in women with T2DM, using high throughput 16S rRNA gene sequencing & enhanced quantitative urine culture (EQUC), and determine the FUM's association with LUTS in women with T2DM. (2) To determine the impact of glycemic control on LUTS and the FUM composition in women with T2DM.

Secondary Objective: To determine whether there is an association between vitamin D status (sufficient, insufficient, and deficient), the FUM and LUTS in women with T2DM.

Exploratory Aim: To examine the relationship of the phage activity with glycemic control, and Urine PH in biobanked urine samples in the laboratory of [name]. Protocol additions from [name] lab included in Modifications included in section

Table of Contents

I. Significance.....	4-5
II. Innovation.....	5-6
III. Conceptualization.....	6
IV. Preliminary Studies.....	6-8
V. Approach.....	8-16
a. Design.....	8-9
b. Sample.....	9-10
c. Procedures.....	10-11
d. Measurements.....	11-14
e. Data management and Analysis.....	15-17
f. Potential Problems and Alternative Solutions.....	17
g. Timeline.....	17
VI. Protection of Human Subjects.....	18-22
VII. References.....	22-33

I. Significance.

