For the analysis of the quantitative measures, descriptive statistics will be used to generate information that will allow for exploring the relationship of these measures to the other study variables being collected (e.g., severity of depression and diabetes) (**Aim 2**). The descriptive data will also allow comparison of these data to other studies that have used these tools. Reliability will be established for each tool at each time point using Cronbach alpha. The current analysis will test *The Global Family Quality of Life Scale-Adult Women Version* and detail its psychometric properties, specifically construct validity and reliability. Descriptive statistics will include mean age, gender, level of education, race and ethnicity. Data from total sample will be analyzed. Regression analysis will be used to address **Aims 2 and 3**. Mediation analyses will be used as appropriate

2. For the sub-study on the Urinary Microbiome, the following analysis was proposed.

Primary Objectives

(1) To determine the FUM composition in women with T2DM using high throughput 16S rRNA gene sequencing & enhanced quantitative urine culture (EQUC), and to determine the FUM's association with LUTS in women with T2DM.

Hypothesis: Among women with T2DM, their FUM composition is a salient predictor of LUTS.

Planned Analyses: To test this hypothesis, LUTS is the response variable and FUM is the primary explanatory variable. FUM will be measured in at least two ways: First as a microbial diversity index (e.g., Shannon, Chao 1) and as an individual microbial taxa count. When diversity indices are used, a log transformation may be applied to adjust for heterogeneity or lack of linearity.

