In this repeated measures study (baseline, 3, and 6 months), a linear mixed effects model will be used to estimate the effect of FUM on patients' LUTS severity score while allowing random intercepts for each participant to account for the within subject correlation engendered by the repeated measurements. Since we are documenting UTIs over the trial, we will also explore the odds of experiencing at least one UTI, to be estimated as a function of the FUM using a generalized linear mixed effects model that also allows random intercepts for each participant; a binomial distribution with logit link will be specified to determine the odds ratio for the FUM diversity index and microbial taxa count. In these models, extreme error variances will be monitored using the ratio of the Pearson chi-square fit statistic over its degrees of freedom. When necessary, UTI may be treated as a count variable

(particularly if there are enough participants experiencing multiple UTI events) and a Poisson distribution with negative binomial link may be used to adjust for observed overdispersion.

(2) To determine the impact of glycemic control on the LUTS and FUM composition in women with T2DM.

Hypothesis: In women with T2DM, the effect of FUM on LUTS *depends* on glycemic control (HBA1C), which may be measured as a continuous or binary (i.e., >7% versus ≤ 7%) variable.

Planned Analyses: Testing this hypothesis is largely a continuation of the investigation specified in prior objective, except that each model will evaluate if any effect of the FUM on LUTS severity *depends* on women's level of glycemic control. Consequently, for this aim, an interaction term between FUM and glycemic control will be estimated for each model specified above. If the interaction is not significant, adjusted estimates will be provided for the effect of FUM on LUTS after controlling for the effect of glycemic control, as well as other salient covariates (e.g., race, age, depression level, body mass index, and concomitant medications).

For both hypotheses, all comparisons, including all possible pairwise interaction terms, will be evaluated using an alpha level of 0.05 and the tests will be two tailed, meaning that an effect in either direction will be interpreted.

Secondary Objective:

To determine whether there is an association between vitamin D status (sufficient, insufficient, and deficient), LUTS, and the FUM.

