Hypothesis (a): Women with T2DM who have less vitamin D will have will have a different FUM composition than those with sufficient vitamin D.

Hypothesis (b): Women with T2DM who have less vitamin D will have will have more LUTS than those with sufficient vitamin D.

Planned Analyses: For this secondary objective, a generalized linear mixed effects model will be used to determine the odds of at least one UTI as a function of ordinal vitamin D status (deficient, insufficient, and sufficient), again allowing random intercepts for each participant to account for within subject correlation due to repeated measurements; these models will specify a binomial distribution with logit link to determine the odds ratio for each pairwise comparison of vitamin D status. As before, extreme error variances will be monitored using the ratio of each model's Pearson chi-square fit statistic over its degrees of freedom. When necessary, a negative binomial link may be used to account for observed over-dispersion. Finally, a linear mixed effects model will be used to estimate the effect of ordinal vitamin D status on patients' FUM indices and microbial taxa count as well as their LUTS symptom severity score, again allowing random intercepts for each participant. For this objective, all model terms will be evaluated using an alpha level of 0.05 and the tests will be two tailed, meaning that an effect in either direction will be interpreted.

To compare vitamin D, LUTS and the FUM, each individual will function as her own control, with the first time point establishing the baseline FUM profile with which to compare the effect of treatment dose at 6 months (endpoint of trial). We will model the outcome using a GLMM, which takes into account the correlation between 2 observations on the same woman. We will determine if there is a change in a women's FUM baseline to end of study by treatment. We will use similar procedures to determine treatment group differences. Similar data analyses will be conducted on the urinary symptoms reported by each participant across time points and between groups.

Exploratory Aim: To examine the relationship of the phage activity with glycemic control, other labs including Urine PH in biobanked urine samples in the laboratory of [name].

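### Microbiome primary objective 2 names FUM composition as an outcome of glycemic control, but no prespecified model has FUM as response and HbA1c as predictor

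*Combined protocol and SAP*

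**What the plan says.** The objective appears twice in the combined protocol and SAP. The Updated Aims section has "To determine the impact of glycemic control on LUTS and the FUM composition in women with T2DM". The urinary microbiome part of section V.5.b (Data Analysis) repeats it almost unchanged: "To determine the impact of glycemic control on the LUTS and FUM composition in women with T2DM".

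The hypothesis placed under it in V.5.b is narrower. It says that the effect of FUM on LUTS depends on HbA1c, "which may be measured as a continuous or binary (i.e., >7% versus ≤ 7%) variable". The analysis follows the hypothesis: "an interaction term between FUM and glycemic control will be estimated for each model specified above". Those earlier models belong to primary objective 1, where "LUTS is the response variable and FUM is the primary explanatory variable". A second, exploratory model has UTI as response: "we will also explore the odds of experiencing at least one UTI, to be estimated as a function of the FUM".

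Should that test fail to reach significance, the plan promises this instead: "adjusted estimates will be provided for the effect of FUM on LUTS after controlling for the effect of glycemic control". Further covariates named there include race, age, depression level, body mass index and medications. Tests are two-sided at 0.05.

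**The concern.** The objective treats glycemic control as the exposure and asks what it does to two things. The planned test asks whether HbA1c changes the slope of LUTS on FUM. These are different quantities. HbA1c could shift the microbiome strongly with no interaction, and an interaction could exist with no shift.

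At stake is whether the sub-study can answer one of its two primary objectives. The randomised comparison, the CES-D outcome and safety are not affected.

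**Working it through.** **Step 1. Response and predictor of every microbiome analysis in V.5.b.**

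| Analysis | Response | Main predictor | Role of HbA1c |
|---|---|---|---|
| Primary objective 1 | LUTS severity | FUM (diversity index, taxa count) | none |
| Primary objective 1, exploratory | UTI (any, or count) | FUM | none |
| Primary objective 2 | LUTS severity; UTI | FUM × HbA1c | moderator |
| Primary objective 2, interaction not significant | LUTS | FUM | covariate |
| Secondary objective | UTI; LUTS severity | vitamin D status | none |
| Secondary objective | FUM indices, taxa counts | vitamin D status | none |
| Secondary objective, own-control comparison | FUM; urinary symptoms | treatment, baseline to 6 months | none |
| Exploratory aim | phage activity, no model given | glycemic control, other labs | correlate |
| Other exploratory | FUM against women without diabetes | diabetes status | none |

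FUM is a modelled response under the secondary objective ("a linear mixed effects model will be used to estimate the effect of ordinal vitamin D status on patients' FUM indices and microbial taxa count") and in the own-control comparison. Neither has HbA1c as predictor. The exploratory aim concerns phage activity, not FUM composition. The comparison with other cohorts concerns having diabetes, not its control.

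**Step 2. What the planned coefficients measure.** Let H be HbA1c, F a FUM index and Y LUTS severity:

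- F = c + g·H + error
- Y = a + b1·F + b2·H + b3·F·H + error

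The FUM half of objective 2 asks for g. The planned test is of b3 = 0, and g does not enter it. In the interaction model, b2 is the HbA1c effect at F = 0. If b3 = 0, the total HbA1c effect on LUTS is b2 + g·b1, whereas a model that also contains F returns b2 alone. For example, with assumed standardised values g = 0.3, b1 = 0.3 and b2 = 0, the total effect is 0 + 0.3 × 0.3 = 0.09 and the adjusted coefficient is 0.

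**Step 3. Illustration.** The plan states no figure to reproduce. All inputs here are assumptions: 150 women, one record each, ordinary least squares, b1 = 0.3, b2 = b3 = 0, two-sided 0.05, 4000 replicates.

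| HbA1c–FUM correlation | Interaction test rejects | Direct model of FUM on HbA1c rejects |
|---|---|---|
| 0 | 4.7% | 5.0% |
| 0.3 | 5.1% | 96.4% |
| 0.5 | 4.8% | 100% |
| 0.8 | 4.7% | 100% |

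Hand check by Fisher's z at correlation 0.3: atanh(0.3) = 0.3095; 0.3095 × √147 = 3.753; 3.753 − 1.960 = 1.793; Φ(1.793) = 0.963, in agreement.

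Across an assumed 100 to 180 women the same formula gives:

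- 100 women: 0.3095 × √97 − 1.960 = 1.088, power 86%
- 180 women: 0.3095 × √177 − 1.960 = 2.158, power 98%

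For LUTS on HbA1c without FUM, under full mediation, the correlation is 0.3 × 0.3 = 0.09 or, with a FUM–LUTS correlation of 0.5, 0.3 × 0.5 = 0.15:

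- 100 women, 0.09: 0.0902 × √97 − 1.960 = −1.071, power about 14%
- 180 women, 0.15: 0.1511 × √177 − 1.960 = 0.051, power about 52% (53% by simulation)

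**The case against.** The best reply is that the hypothesis shows what was meant. V.5.b states moderation explicitly and the interaction model tests it correctly, so the fault may lie in the objective's wording. That is possible and would be a legitimate resolution. But the objective is worded the same way in two sections, so the text still has to be reconciled.

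A reader might infer that the HbA1c–FUM association is never looked at. The documents do not support that. Section V.5.a promises bivariate analyses and correlations for all variables, which read literally would include this pair. Those are preliminary checks, not tied to objective 2, and they make no provision for repeated measures or covariates. What stands is that no model is prespecified.

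A reader might also infer that HbA1c's effect on LUTS goes unestimated. That too is too strong. The fallback model includes HbA1c, and an interaction model would normally carry its main effect, so a coefficient would be fitted. The plan does not name it as a result. It differs from the total effect only if part of the effect runs through FUM, a pathway that the documents do not assert.

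Finally, the simulation sets moderation and the direct HbA1c effect to zero. The 5% rejection rate is therefore built in, and one record per woman is not the planned random-intercept model. It shows the logic and does not measure harm in this study.

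**Conclusion.** The point holds for FUM composition: a stated primary objective of the sub-study has no prespecified model that addresses it. This rests on reading the response and predictor of each analysis, not on any simulated figure. For LUTS the gap is smaller: a coefficient would exist, but it is unnamed and conditional on FUM.

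The powers of 86% to 98% (FUM on HbA1c) and 14% to 52% (LUTS on HbA1c) depend on assumed correlations and an assumed 100 to 180 women. The documents give no microbiome sample size, and the study-visit procedures say only that urine may be requested. One might infer that the sub-study would report no impact of glycemic control. Nothing in the documents says so: after a non-significant interaction they call for adjusted FUM–LUTS estimates, not for that conclusion.

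**What to change.** For primary objective 2:

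1. Add a random-intercept mixed model using the 0, 3 and 6 month data, with one named FUM measure (for example the Shannon index) as response and HbA1c, visit, arm and the covariates already listed as predictors. Take the HbA1c coefficient as the test, and say whether HbA1c enters as continuous or split at 7%.
2. Label other diversity indices and taxa counts as exploratory.
3. Report the HbA1c effect on LUTS severity from a model with the same terms and without FUM.
4. Keep the FUM-by-HbA1c interaction as a separately labelled moderation hypothesis.

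If only moderation was intended, restate objective 2 as effect modification in both the Updated Aims and V.5.b.

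The measurement table already schedules HbA1c and urine at 0, 3 and 6 months, so no new data are needed. The cost is plan wording and a few more tests at 0.05 in a sub-study that states no multiplicity control. Because FUM is to be measured in at least two ways, the added tests stay few only if one measure is named in advance. Under the assumptions above, the LUTS model may also have low power.
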